6.1.3. Product Storage and Stability

The valacyclovir caplets should be stored at 15° – 25° C (59° – 77° F). Adherence to the USP Controlled Room Temperature is required. After constituting the study drug, it can be used within 21 days of preparation. The constituted study drug should be stored under refrigeration (2° – 8° C or 36° – 46° F) in a refrigerator. The constituted study drug must not be frozen.

6.2 6.2. Dosage, Preparation and Administration of Study Investigational Product

The dose of valacyclovir to be evaluated is 20 mg/kg every 8 hours to correlate with 20 mg/kg every 8 hours of intravenous acyclovir that is already used as standard of care for treatment of neonatal HSV disease. The subject enrolled in the study will receive anywhere from 2 up to 7 days (6-21 doses) of valacyclovir depending upon availability of the CHRU.

6.2.1. Preparation of Study Drug

Valacyclovir extemporaneously oral suspension will be reconstituted by COA's research or designated pharmacist. The extemporaneous suspension will be prepared following the instructions from the American Society of Health-System Pharmacists.

6.2.2. Administration of Study Drug

Valacyclovir may be given with or without food. The route of administration of study drug will be recorded (orally, nasogastric tube, orogastric tube, etc.).

6.3 6.3. Drug Accountability

After receipt of the investigational drug, the pharmacist will be responsible for and maintain logs of receipt, dispensation, storage conditions, and disposal of study drug. All original documents will be provided to the PI and will be maintained in a secure and accessible location.

Used and unused study product will not be disposed of or returned until the study monitor reviews and confirms the drug accountability.

- Used or partially used study product will be disposed of by the local site pharmacy in accordance with local regulations after completion of drug accountability by the study monitor.

6.4 6.4. Concomitant Medications

Concomitant medications not be recorded as this is only a PK sampling study.

6.5 6.5. Prohibited Medications

No drugs are prohibited while taking valacyclovir as there are no clinically significant drug-drug interactions.

7 STUDY SCHEDULE

7.1 Screening

Potential subjects will be identified by the site investigators and the study coordinators. Informed consent signed by study subject's parent(s) or guardian(s) must be obtained prior to study enrollment.

7.2 Enrollment/Baseline

7.2.1. Baseline Assessment (Window: Treatment Day 1 through Treatment day 14)

- Confirm that informed consent has been obtained from parent or legally authorized representative
- Document baseline demographics
 - Gestational age at delivery
 - Date of birth
 - Day of life at initiation of IV acyclovir therapy
 - Gender
 - Race
 - Ethnicity
 - Birth weight
 - Weight at enrollment
 - Length in centimeters at enrollment
 - Type of neonatal HSV
 - HSV diagnostic results (surface culture and/or PCR, HSV CSF PCR, HSV blood PCR, and/or lesion culture and/or PCR)
- Hematology labs
 - WBC with differential drawn for clinical purposes will be recorded
- Chemistry labs
 - All creatinine and alanine aminotransferase (ALT) values obtained for clinical purposes will be recorded

7.3 Study Follow-up

7.3.1. Period 1 (Treatment Day 1 through Treatment Day 7)

- Hematology labs

- WBC with differential will be recorded if being drawn for clinical reasons (any laboratory value obtained during the window will suffice, with an effort being made to capture the most abnormal value)
- Chemistry labs
 - Creatinine and alanine aminotransferase (ALT) values will be recorded if being drawn for clinical reasons
- Acyclovir pharmacokinetics
 - A single blood sample for PK determination will be obtained daily at random time intervals as able
 - Timepoints for pharmacokinetic draws will occur at random time intervals
 - Date and time of lab draw for PK specimen will be recorded
 - Date and time of last acyclovir infusion prior to PK lab draw will be recorded
 - Most recent patient weight, acyclovir dose received, and serum creatinine value will be recorded
 - Required amount of whole blood for plasma acyclovir determination at each timepoint is 200 μ L (0.2 mL)

Note: blood for PK assessments will be obtained at the time that a clinical blood draw is being performed, or through the indwelling intravenous catheter, so that no additional venipuncture procedures solely for study purposes will be required

7.3.2. Period 2 (Treatment Day 8 through Treatment Day 14 for SEM disease and Treatment Day 21 for CNS and disseminated disease)

- Hematology labs
 - WBC with differential will be recorded if being drawn for clinical reasons (any laboratory value obtained during the window will suffice, with an effort being made to capture the most abnormal value)
- Chemistry labs
 - Creatinine and alanine aminotransferase (ALT) values will be recorded if being drawn for clinical reasons
- Acyclovir pharmacokinetics
 - One acyclovir PK sampling profile will be performed after dose 22 and before dose 42
 - Acyclovir concentrations will be obtained at specified timepoints
 - Timepoints for pharmacokinetic draws: 0h (within 30 minutes prior to the start of the infusion of acyclovir), within 15 minutes after completion of the infusion, and 3-4 hours after infusion
 - Most recent patient weight, acyclovir dose received, and serum creatinine value will be recorded
 - Required amount of whole blood for plasma acyclovir determination at each timepoint is 200 μ L (0.2 mL)

Note: blood for PK assessments will be obtained at the time that a clinical blood draw is being performed, or through the indwelling intravenous catheter, so that no additional venipuncture procedures solely for study purposes will be required

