2.3 Potential Risks and Benefits

2.3.1 Potential Risks

One potential risk relates to the blood draws (e.g., bruising at the site, discomfort, infection) required to obtain the pharmacokinetic samples. All infants should have a long-term indwelling intravenous catheter (e.g. PICC) during hospitalization for administration of IV acyclovir through which blood can be withdrawn without risk of discomfort from a needle stick or bruising at the site during or after the blood drawing and rarely infection. However, once the infant is discharged from the hospital the indwelling intravenous catheter will need to be removed to prevent more harm to the infant as the risk of infection is greater when an indwelling catheter is not being used. Thus, valacyclovir pharmacokinetic samples will need to be obtained via a heel or venous stick on day 2 up to day 7 of valacyclovir therapy. Heel warmers or socks can be used prior to the blood draw to increase blood flow to the heel and reduce the amount of discomfort experienced with squeezing of the infant's heel in order to obtain the amount of blood necessary. The weight-based volumes required for the study-specific procedures are less than the limits of the Institutional Review Board and the NIH.

Additionally, daily random pharmacokinetic samples obtained during the first week of IV acyclovir will be obtained only at the time of clinical blood draws (creatinine and/or CBC/diff) to prevent additional venipuncture procedures solely for study purposes. The weight-based volumes required for the study-specific procedures are less than the limits of the Institutional Review Board and the NIH.

Potential risks associated with the use of valacyclovir are comparable to the risks associated with long term use of the current standard of care, oral acyclovir. Therefore, monitoring for adverse events is not necessary for short term use (2 and up to 7 days) of valacyclovir.

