4 STUDY DESIGN

This study is an open-label, single-center, pharmacokinetic study of valacyclovir pharmacokinetics in male and female infants \geq 34 weeks gestation, \leq 42 days of age at initiation of intravenous acyclovir, and \geq 2000 g who have been diagnosed with virologically confirmed neonatal HSV disease via culture or polymerase chain reaction (PCR). Infants who meet the inclusion criteria will be eligible for the study, and informed consent will be obtained by the infant's parent(s) or legal guardian(s).

Subjects meeting enrollment criteria will be enrolled in this clinical trial. The total sample size will be 6 and up to 10 infants diagnosed with any of the 3 disease classifications of neonatal HSV disease. Following enrollment, infants during the first week of treatment with intravenous acyclovir as per standard of care will have daily random pharmacokinetic levels (population based pharmacokinetics) obtained at the same time of clinical blood draws (e.g. creatinine and/or CBC/diff), namely using remnant specimens. During the second week of treatment with IV acyclovir (between dose 22 and 42) infants will have one pharmacokinetic sampling profile obtained. The plasma specimens for the pharmacokinetic sampling profile will be drawn immediately prior to next dose (within 30 minutes prior to the start of infusion and 8 hours after previous dose) for an 8 hour trough, a post-infusion peak obtained within 15 minutes following completion of infusion, and 3-4 hours after infusion. Once these samples are obtained, the infant will complete the course of IV acyclovir per the standard of care guidelines.

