7.3.3. Period 3 (Day 2 and up to 7 of valacyclovir)

- Valacyclovir pharmacokinetics
 - One valacyclovir PK sampling profile will be performed on Day 2 (and up to day 7) of valacyclovir
 - Acyclovir concentrations will be obtained at specified timepoints
 - Timepoints for pharmacokinetic draws: 0h (immediately prior to valacyclovir dose; window: -15 min), 1-2 hours after dose, and 3-5 hours after dose
 - Date and time of last valacyclovir dose prior to PK lab draw will be recorded
 - Date and time of valacyclovir dose given in the CHRU will be recorded
 - Required amount of whole blood for plasma acyclovir determination at each timepoint is 200 μ L (0.2 mL)

Note: blood for PK assessments will be obtained either via venous/heel stick; will attempt to reduce discomfort experienced with heel sticks by using a heel warmer prior to blood draw

- Initiation of oral acyclovir per standard of care guidelines to complete 6-month course of oral suppressive therapy at recommended dose of 300 mg/m²/dose every 8 hours) after last PK lab is drawn. Prescription for oral acyclovir to be written and prescription filled by outpatient pharmacy and billed to patient's insurance prior to leaving the hospital

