8 STUDY PROCEDURES/EVALUATIONS

The study procedures and evaluations are summarized in Appendix A: Schedule of Events. In the conduct of this study, hospital staff may perform research activities (e.g., pharmacokinetic blood draw collection) under the direction of the Principal Investigator or designee.

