8.2.1.1. Acyclovir Pharmacokinetics

Assessment of acyclovir plasma concentrations will be conducted at the UAB Pharmacokinetic Laboratory. Acyclovir concentrations will be obtained on a daily basis at random time intervals during Period 1 (Treatment Day 1 through Treatment Day 7). One PK sampling profile will then be completed during Period 2 (between Treatment Day 8 and Treatment Day 14). Timepoints for pharmacokinetic draws for Period 2 are as follows: 0 hours (within 30 minutes prior to the start of the infusion), within 15 minutes after completion of the infusion, and 3-4 hours after infusion.

Pharmacokinetic specimens will also be obtained during Period 3 (Day 2 up to Day 7 of valacyclovir). The timepoints for the lab draws for Period 3 are as follows: 0 hours (just prior to the enteral dose of valacyclovir and approximately 8

hours after previous dose), 1-2 hours after dose, and 3-5 hours after dose. The required amount of whole blood for plasma acyclovir determination at each time point is 200 μ L (0.2 mL). Specimens will be processed to separate the plasma, and then will be transported to the UAB Pharmacokinetic Laboratory. Most recent patient weight, valacyclovir dose received, timing of dose, sample collection time, WBC, percentage neutrophils, ANC, ALT, and serum creatinine value will be recorded.

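### Could taking the Period 2 peak through the catheter that delivers acyclovir bias the IV AUC8?

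*Combined protocol and SAP*

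**What the plan says.** Section 2.3.1 expects every infant to have a long-term "catheter (e.g. PICC) during hospitalization for administration of IV acyclovir through which blood can be withdrawn". The note closing Section 7.3.2 allows Period 2 PK blood to be collected at a clinical draw "or through the indwelling intravenous catheter, so that no additional venipuncture procedures solely for study purposes will be required"; the same note closes Section 7.3.1. It makes no exception for any of the three Period 2 samples, one of which Section 4 describes as "a post-infusion peak obtained within 15 minutes following completion of infusion".

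On data capture, Section 7.3.2 states: "Most recent patient weight, acyclovir dose received, and serum creatinine value will be recorded". Section 8.2.1.1 adds, among other items, "valacyclovir dose received, timing of dose, sample collection time". Draw site is in neither list. Section 8 says that "hospital staff may perform research activities (e.g., pharmacokinetic blood draw collection) under the direction of the Principal Investigator or designee".

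The oral profile is collected differently. In Section 7.3.3, "blood for PK assessments will be obtained either via venous/heel stick".

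Section 11.4 derives the parameters by non-compartmental analysis and compares mean AUC8 between the oral and IV profiles with 95% confidence intervals.

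**The concern.** A sample taken through a line that has just carried the drug can pick up residual infusate and read high. If the line was flushed and not cleared, the sample can be diluted and read low. The Period 2 peak is the sample most open to carry-over, because it comes minutes after the infusion ends. It is also one of only three points behind IV AUC8, Cmax, CL and Vd.

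The oral samples come from a vein or heel, so a catheter error would not cancel in the within-infant comparison. A falsely high IV peak would make oral exposure look too low. A falsely low one would make the two routes look alike when they are not. The comparison is a secondary endpoint in Section 3.2.2, but Sections 11.1 and 11.2 treat it as the main question, and Section 2.2 says earlier high-dose IV data come from only two patients. With no draw site recorded, an odd peak would be hard to interpret later.

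**Working it through.** **What the text does and does not establish**

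- Shared catheter: established by reading Section 2.3.1 with the note in Section 7.3.2.
- Catheter sampling: permitted, not required.
- Number of lumens, infusion time and infusate concentration: not given.
- Line-clearing rule: not in the protocol text available. The contents list a Section 8.2.2 on specimen preparation and handling whose body is not in that text, and Section 10.1 refers to study manuals that are not part of it. Absence of a rule cannot be shown.
- Recorded items: Section 15 says the eCRFs are still to be developed, so the lists in Sections 7.3.2 and 8.2.1.1 need not be complete.

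**Blood volume.** 3 samples × 0.2 mL = 0.6 mL, the Period 2 total in Appendix A. That row covers assay blood and shows no discard volume. Section 2.3.1 says the weight-based "volumes required for the study-specific procedures are less than the limits of the Institutional Review Board and the NIH".

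**How an error in the peak would pass into AUC8.** The plan has no figure to reproduce, so this is a scenario. Assumptions, none from the documents: one compartment at steady state, 1 h infusion every 8 h, half-life 2, 3 or 4 h, samples at 0, 1.125 and 4.5 h from the start of infusion, and only the peak mis-measured.

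Under the linear trapezoid with the 8 h value set equal to the trough, the peak carries weight (4.5 − 0)/2 = 2.25 h. With the true peak scaled to 1, AUC8 is 3.53, 4.30 and 4.87 for half-lives of 2, 3 and 4 h. The peak's share is therefore 2.25/3.53 = 64%, 2.25/4.30 = 52% and 2.25/4.87 = 46%. The change in AUC8 is the peak error times that share; for example, 50% × 0.64 = 32%.

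Section 11.4 fixes neither the trapezoid rule nor the source of the 8 h value, so three versions are shown (range over the three half-lives):

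| Peak error | Linear, C8 = trough | Linear-up/log-down, C8 = trough | Linear-up/log-down, C8 extrapolated from last two samples |
|---|---|---|---|
| +10% | +4.6 to +6.4% | +4.1 to +5.4% | +2.8 to +4.6% |
| +25% | +11.6 to +15.9% | +10.1 to +13.2% | +7.1 to +11.5% |
| +50% | +23.1 to +31.9% | +19.8 to +26.0% | +14.6 to +23.1% |
| −10% | −4.6 to −6.4% | −4.2 to −5.5% | −2.6 to −4.6% |
| −50% | −23.1 to −31.9% | −22.2 to −28.7% | −9.4 to −21.7% |

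The oral/IV ratio changes by 1/(1 + x) − 1. At x = +31.9% that is −24%; at x = −31.9% it is +47%. If flush diluted all three samples equally, AUC8 would fall by the full dilution fraction.

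**Effect on the mean.** If one profile has a peak 50% too high and the AUC8 values are otherwise equal, the mean rises by (14.6 to 31.9%)/6 = 2.4 to 5.3% with 6 infants, or (14.6 to 31.9%)/10 = 1.5 to 3.2% with 10. If every profile were affected, the mean would move by the full per-profile amount.

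**How visible it would be.** In a 0.2 mL sample, 1 µL of infusate at an assumed 50 to 500 times the blood level adds (0.001/0.2) × 49 = 24.5% up to (0.001/0.2) × 499 = 249.5%. The upper end would show as an implausible Vd or CL. Errors of 10% to 25% might not.

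**Would extra analysis help?** A by-site listing needs variation in draw site, but Section 2.3.1 expects all infants to have the catheter. A sensitivity summary without contaminated profiles needs a record of contamination, which draw site alone does not give. Dropping a profile also costs precision: t(0.975, n−1)/√n goes from 1.049 to 1.242 SD units for 6 to 5 infants (+18%) and from 0.715 to 0.769 for 10 to 9 (+7.5%). A rule for Period 1 could not choose the lumen, because Section 4 describes those samples as mainly leftover clinical blood.

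**The case for a change.** The strongest case for acting is that catheter sampling will probably be the usual route. The note rules out venipuncture done only for the study, and three timed samples will seldom all coincide with clinical draws. Hospital staff may collect them, which makes a written rule more useful. Any error falls on one side of the comparison, and the peak carries about half or more of the linear AUC8. The Protocol Summary also allows subjects with inadequate sampling to be replaced. If draw conditions are unknown, that judgement could rest on the concentration itself, which is an uncomfortable basis for exclusion among 6 to 10 infants. One instruction and one data field cost little.

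The textual facts and the one-sidedness stand, and so does the sensitivity of AUC8 to the peak. What is missing is any sign that a sample would be drawn from an uncleared line. Flush dilution would also spoil creatinine and blood counts taken through the same catheter, so the site has its own reason to clear it. The replacement worry is softened because clinical records may show how a sample was drawn.

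**Conclusion.** No change to the plan is needed. The protocol leaves a bedside sampling step unwritten, and a team that clears the line, or uses another lumen where there is one, fills that gap without touching the design or the analysis. Sections 2.1 and 2.2 describe a centre experienced in such studies and a laboratory set up for small blood specimens.

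The size of any error cannot be found from the documents and may be zero. The percentages above describe a profile already assumed to be affected; they do not estimate bias in this trial. The valacyclovir AUC8 listed as primary in Section 3.2.1 does not depend on catheter sampling.

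This conclusion assumes that blood is drawn through the catheter only after ordinary line clearing. If that assumption failed across most infants, IV AUC8 and the oral/IV comparison would be affected by the full per-profile amounts. That is a matter for the sampling procedure, and the added listing and sensitivity summary would not detect or correct it.

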7.3.3. Period 3 (Day 2 and up to 7 of valacyclovir)

- Valacyclovir pharmacokinetics
 - One valacyclovir PK sampling profile will be performed on Day 2 (and up to day 7) of valacyclovir
 - Acyclovir concentrations will be obtained at specified timepoints
 - Timepoints for pharmacokinetic draws: 0h (immediately prior to valacyclovir dose; window: -15 min), 1-2 hours after dose, and 3-5 hours after dose
 - Date and time of last valacyclovir dose prior to PK lab draw will be recorded
 - Date and time of valacyclovir dose given in the CHRU will be recorded
 - Required amount of whole blood for plasma acyclovir determination at each timepoint is 200 μ L (0.2 mL)

Note: blood for PK assessments will be obtained either via venous/heel stick; will attempt to reduce discomfort experienced with heel sticks by using a heel warmer prior to blood draw

- Initiation of oral acyclovir per standard of care guidelines to complete 6-month course of oral suppressive therapy at recommended dose of 300 mg/m²/dose every 8 hours) after last PK lab is drawn. Prescription for oral acyclovir to be written and prescription filled by outpatient pharmacy and billed to patient's insurance prior to leaving the hospital

7.4 Early Termination Visit

Study subjects may withdraw voluntarily from participation in the study at any time. If a study subject withdraws or is discontinued from the study at any time prior to completion of the study, the reason for this decision will be recorded on the eCRFs. SAEs and AEs will be followed according to guidelines in Section 9. Upon withdrawal from the study, the infant should follow the standard of care guidelines for neonatal HSV disease.

7.5 Unscheduled Visit

Should an unscheduled visit occur, the study subject will be assessed as standard of care.

8 STUDY PROCEDURES/EVALUATIONS

The study procedures and evaluations are summarized in Appendix A: Schedule of Events. In the conduct of this study, hospital staff may perform research activities (e.g., pharmacokinetic blood draw collection) under the direction of the Principal Investigator or designee.

8.1 Clinical Evaluations

8.1.1. Baseline Demographics

To characterize the study subjects, information will be recorded at the baseline study visit following the obtaining of informed consent. Data collected will include basic demographics and birth history (date of birth; gestational age at delivery; gender; race; ethnicity; birth weight; weight at enrollment; length in centimeters at enrollment; all HSV diagnostic tests, CSF indices from lumbar puncture(s); classification of neonatal HSV disease, age at diagnosis; day of life at initiation of IV acyclovir therapy; acyclovir dose and dosing frequency).

8.2 Laboratory Evaluations

All chemistry labs (serum creatinine, ALT) will be recorded on eCRFs if they have been drawn for clinical reasons; only the most abnormal value for hematology labs (WBC with differential) will be recorded on eCRFs if they have been drawn for clinical reasons

8.2.1 Special Assays or Procedures

Research assays (Pharmacokinetics will be conducted at the respective UAB lab).

8.2.1.1. Acyclovir Pharmacokinetics

Assessment of acyclovir plasma concentrations will be conducted at the UAB Pharmacokinetic Laboratory. Acyclovir concentrations will be obtained on a daily basis at random time intervals during Period 1 (Treatment Day 1 through Treatment Day 7). One PK sampling profile will then be completed during Period 2 (between Treatment Day 8 and Treatment Day 14). Timepoints for pharmacokinetic draws for Period 2 are as follows: 0 hours (within 30 minutes prior to the start of the infusion), within 15 minutes after completion of the infusion, and 3-4 hours after infusion.

Pharmacokinetic specimens will also be obtained during Period 3 (Day 2 up to Day 7 of valacyclovir). The timepoints for the lab draws for Period 3 are as follows: 0 hours (just prior to the enteral dose of valacyclovir and approximately 8

hours after previous dose), 1-2 hours after dose, and 3-5 hours after dose. The required amount of whole blood for plasma acyclovir determination at each time point is 200 μ L (0.2 mL). Specimens will be processed to separate the plasma, and then will be transported to the UAB Pharmacokinetic Laboratory. Most recent patient weight, valacyclovir dose received, timing of dose, sample collection time, WBC, percentage neutrophils, ANC, ALT, and serum creatinine value will be recorded.

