Description of Study Design:	
This is an open-label, single center, PK study to assess valacyclovir pharmacokinetics and pharmacodynamics in neonates and compare to the pharmacokinetics and pharmacodynamics of the standard of care treatment dose of intravenous acyclovir. Only those babies with virologically confirmed neonatal HSV disease will be enrolled in the study. The decision to initiate valacyclovir for 2 (up to 7) days will be made by a physician based on inclusion/exclusion criteria, and those who meet entry criteria will be eligible for the study. Those enrolled in the study will have daily random parenteral acyclovir PK levels drawn during the first week of treatment (drawn only at times of other lab draws). These infants will also have a pharmacokinetic sampling profile obtained on or after dose 22 and before dose 42 of intravenous acyclovir. The PK samples for the sampling profile will be collected just prior to the next dose of intravenous acyclovir (within 30 minutes prior to the start of the infusion), within 15 minutes of completion of the infusion, and 3-4 hours after infusion. Upon completion of the recommended treatment course duration with intravenous acyclovir determined by disease classification (SEM, CNS, or disseminated disease), the infant will be started on enteral valacyclovir 20 mg/kg every 8 hours.
 
On day 2 and no more than day 7 of valacyclovir 20 mg/kg every 8 hours, a pharmacokinetic sampling profile will be obtained. The PK samples will be collected just prior to the

enteral dose of valacyclovir hour 0 (8 hours after previous dose and immediately before next dose), 1-2 hours after dose, and 3-5 hours after dose.

Subjects with inadequate pharmacokinetic data for analysis (e.g., due to dropping out of the study before PK assessments are performed, or blood sampling obtained but is inadequate for analysis) may be replaced and will not count toward the total of 6 (and up to 10) subjects.

Estimated Time to Complete Enrollment: 4.5 years from enrollment of the first study subject

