Currently the standard of care requires that infants diagnosed with neonatal HSV disease are treated with high dose intravenous acyclovir for 14-21 days depending on classification of the disease (6, 13); infants with SEM disease are recommended to receive 14 days of intravenous acyclovir whereas infants with CNS and disseminated disease are recommended to receive at least 21 days of intravenous therapy. Those with CNS disease could potentially require longer than 21 days of therapy as duration of therapy is determined on clearance of viral DNA from the CSF via repeat lumbar puncture performed near the end of the 21 days of therapy(14). If the viral DNA is still detected, intravenous acyclovir is continued for an additional week and another lumbar puncture is performed. Infants remain hospitalized for the entire duration of treatment in order to closely monitor for the potential risk of renal toxicity, a common reversible side effect of intravenous acyclovir. Once the infant has completed the treatment

course of intravenous acyclovir, they are transitioned to oral acyclovir (300 mg/m²/dose three times a day) and discharged home to complete a total of 6 months of suppressive therapy to prevent further neurologic injury by subclinical viral replication (13, 15). Suppressive therapy has significantly improved neurologic outcome (higher neurodevelopmental scores) in those infants with CNS disease and decreased the number of skin recurrences when started immediately after completion of treatment with IV acyclovir (15, 16).

Although vast advancements have been made in the treatment of neonatal HSV disease to reduce mortality and morbidity, there remains a high emotional burden and demand on families as a result of guilt, lengthy hospitalizations, and frequent administration of medications for a prolonged period of time. There is also a large financial burden on healthcare systems; the estimated costs for treatment of neonatal HSV disease accounting for admission and 6 months of follow up in a cohort of 900 infants from 2009-2015 was more than 60 million dollars (4), which will continue to increase as the incidence of the disease increases. Preventing neonatal HSV disease would be ideal to reduce the emotional stress and demand on families and financial burden on healthcare systems, but until that time, other means of reducing these stressors should be evaluated.

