11.4 Final Analysis Plan

Descriptive statistics will be represented by means, standard deviations, and confidence intervals for continuous variables and counts and proportions for categorical variables.

Primary analysis: Acyclovir and valacyclovir pharmacokinetic parameters will initially be determined using non-compartmental analysis (WinNonlin v5.3) for each individual subject. The parameters (AUC_8 , CL, Vd, etc.) will be summarized and further used for exploratory pharmacodynamic analysis.

To compare how the valacyclovir PK as measured by AUC_8 in infants diagnosed with neonatal HSV disease differ from acyclovir PK as measured by AUC_8 in the same subset of patients, we will construct 95% confidence intervals around the mean AUC_8 and compare these means across the subset of patients. Additional pharmacokinetic parameters that compose analyses for secondary endpoints include C_{max} , $T_{1/2}$, CL, and Vd.

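### No laboratory or virology test is scheduled on valacyclovir, so its pharmacodynamics cannot be compared with IV acyclovir and the safety objective cannot see symptomless laboratory toxicity

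*Combined protocol and SAP*

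**What the plan says.** The study title names valacyclovir pharmacodynamics. The design description in the Protocol Summary says the study will assess them and "compare to the pharmacokinetics and pharmacodynamics of the standard of care treatment dose of intravenous acyclovir". Section 11.4 says the PK parameters will be "further used for exploratory pharmacodynamic analysis". Assessing valacyclovir safety is a co-primary objective (Protocol Summary; Section 3.1).

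The collection side is thinner:

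- Section 7.3.3 (Period 3, on valacyclovir): "One valacyclovir PK sampling profile will be performed on Day 2 (and up to day 7) of valacyclovir", sampled before the dose and then "1-2 hours after dose, and 3-5 hours after dose". Unlike Sections 7.3.1 and 7.3.2, it has no hematology or chemistry item.
- Section 8.2.1.1, on what accompanies that profile: "Most recent patient weight, valacyclovir dose received, timing of dose, sample collection time, WBC, percentage neutrophils, ANC, ALT, and serum creatinine value will be recorded".
- Section 8.2: chemistry is recorded if drawn clinically, and "only the most abnormal value for hematology labs (WBC with differential) will be recorded on eCRFs if they have been drawn for clinical reasons".
- Section 4: blood for research is limited to the PK specimens.

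On safety, Section 3.2.1 counts unsolicited events of at least Grade 3, serious events and unresolved events. Section 2.3.1 says "monitoring for adverse events is not necessary for short term use (2 and up to 7 days) of valacyclovir". Section 9.1 repeats this and restricts adverse events, for this protocol, to those linked to blood draws.

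**The concern.** The plan claims results on valacyclovir that its schedule does not supply data for. Three consequences follow.

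1. With no effect variable measured on valacyclovir, there is nothing to compare with IV acyclovir.
2. Section 8.2.1.1 attaches white-cell, neutrophil, ALT and creatinine values to the valacyclovir profile. If those values came from the IV phase, relating them to valacyclovir AUC_8 would relate an exposure to something that happened before it. With 6 to 10 infants, a chance or carry-over pattern could be read as exposure-response.
3. A rise in creatinine or a fall in neutrophils without symptoms would not be seen on valacyclovir. A report of no events could then be taken as reassurance on renal, hepatic or marrow effects that were never examined.

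**Working it through.** **Step 1: reproduce the plan's blood volume for Period 3.** Inputs are three time points (Section 7.3.3) and 0.2 mL per sample (Section 7.3.3; Appendix A).

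3 × 0.2 mL = 0.6 mL

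Appendix A states 0.6 mL for the valacyclovir column. The PK samples use all of it, so nothing is allotted to chemistry, hematology or virology. This agrees with Section 4.

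**Step 2: check the schedule row by row.** In Appendix A as extracted, the hematology and chemistry marks fall under Treatment Days 1 and 7. Merged cells may have shifted them, but neither falls in the valacyclovir column. There is no virology row. The one creatinine condition tied to valacyclovir (Section 5.2, criterion 4) applies before it starts. On-drug values guaranteed by the protocol: 0 of 6 to 10 infants.

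**Step 3: check virology in both phases.** Section 15.3 lists virologic results as a data type, but the virology described is diagnostic testing recorded at baseline (Sections 7.2.1 and 8.1.1). The repeat CSF testing in Section 2.1 is standard care for CNS disease and precedes valacyclovir. No serial virology is planned in either phase.

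**Step 4: how old is a pre-drug value at the profile?** Assume valacyclovir Day 1 is the calendar day of the first dose. A pre-drug value is drawn on or before Day 1, so for a profile on Day d:

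lag ≥ d − 1 calendar days

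| Profile day | Minimum lag |
|---|---|
| 2 | 1 day |
| 7 | 6 days |

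These are ages of the values, not estimates of bias.

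**Step 5: what could a clean result say?** If every infant had one on-drug value and none was abnormal, the one-sided 95% upper bound on the event rate would be 1 − 0.05^(1/n):

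- n = 6: 39.3%
- n = 10: 25.9%

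With no infant measured on drug there is no bound at all.

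**Step 6: set the safety passages side by side.** The Section 3.2.1 endpoint covers events of any origin that meet its criteria. Section 9.1 admits only blood-draw events as adverse events. Under Section 9.1 a Grade 3 laboratory change would not count even if it were measured.

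**The case against.** **Pharmacodynamics is marginal.** It is not an objective or endpoint, Section 11.4 calls it exploratory, and no variable is named. Nowhere does the plan say valacyclovir AUC_8 will be related to neutrophils, ALT or creatinine. Creatinine in Section 8.2.1.1 can naturally be read as a PK covariate, though neutrophils and ALT fit that reading less well. This stands in part: a spurious association is possible, not certain. It does not rescue the promise in the title and design description.

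**On-drug values may exist.** Section 8.2 sets no period limit, so a test ordered by a clinician during valacyclovir could be recorded. This stands: pre-drug values are the default, not a certainty.

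**The IV phase has gaps too.** Its laboratory tests are also recorded only if drawn clinically. A reader might infer that viral measures are missing only on valacyclovir, but serial virology is absent in both phases.

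**The safety endpoint is event-based.** No laboratory endpoint is named, and Section 9.1 would block a laboratory event anyway. This stands, and means that adding tests alone would not repair the safety objective.

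**No-monitoring rationale.** A reader might infer that it contradicts the trial's hypothesis. Section 11.1 expects exposure comparable to IV acyclovir, and Section 2.1 says of IV treatment that "Infants remain hospitalized for the entire duration of treatment in order to closely monitor for the potential risk of renal toxicity". But the documents tie renal toxicity to the intravenous course. They do not say that AUC_8 drives it or that 2 to 7 enteral days carry the same risk. This is a tension to reconcile, not a demonstrated contradiction.

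**Most abnormal values.** Keeping only the most abnormal hematology value might look like a biased rule across the whole study. Section 7.3 and Appendix A make it an effort within a window, where any value suffices. These passages and Section 8.2.1.1 still need one common rule.

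**Conclusion.** The point holds. As written, the schedule guarantees no laboratory or virology value on valacyclovir in any of the 6 to 10 infants. The pharmacodynamic comparison with IV acyclovir, and the exploratory analysis in Section 11.4, cannot be delivered for valacyclovir. By default the values recorded with its profile pre-date it by at least 1 to 6 calendar days, depending on the profile day. The co-primary safety objective cannot detect symptomless laboratory toxicity, and Section 9.1 is separately in conflict with Section 3.2.1.

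This rests on Section 7.3.3 and Appendix A being the full list of Period 3 procedures, on Day 1 being the day of the first dose, and on no clinical draw during valacyclovir. The last is an assumption about practice that the documents cannot settle.

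Two stronger readings are not supported. The documents do not show that any exposure-laboratory finding would be an artefact, because no such analysis is specified. Nor do they show that on-drug tests must be added. That is a monitoring choice, and a single value in 6 to 10 infants would still leave upper bounds of about 39% to 26%.

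**What to change.** 1. Remove the pharmacodynamic comparison from the title, the design description and Section 11.4, or limit it to named variables actually measured on valacyclovir.
2. Record the draw date of every laboratory value listed in Section 8.2.1.1. Exclude values drawn before the first valacyclovir dose from any valacyclovir exposure-response or safety summary. State one recording rule across Sections 7.3, 8.2 and 8.2.1.1 and Appendix A.
3. State that the safety conclusion does not cover renal, hepatic or marrow laboratory toxicity on valacyclovir unless on-drug values are obtained.
4. Reconcile Sections 2.3.1 and 9.1 (risk like that of oral acyclovir, blood-draw events only) with the Section 3.2.1 endpoint and the IV-comparable exposure hypothesis in Section 11.1.

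Whether to add on-drug tests at the existing CHRU visit is for the sponsor to decide within blood-volume limits. The documents give no volume for such tests, so that cost cannot be sized here. Sections 4 and 7.3.3 and Appendix A would have to change with it.

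Items 1 to 4 cost wording and one date field per laboratory value. The downside is a narrower stated conclusion.
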